3.3 Hypothesis Testing and Inferential Analyses

Descriptive statistics will be used to summarize all data. No formal hypothesis testing is planned.

3.4 Multiple Comparisons and Multiplicity Adjustments.

Not applicable for this study.

3.5 Coding of Events and Medications

Adverse event verbatim terms will be coded using the Medical Dictionary for Regulatory Activities (MedDRA) Version 23.0 or the latest version in use. Terms will be coded to the full MedDRA hierarchy, but the system organ class (SOC) and preferred terms (PT) will be of primary interest for the analysis.

Prior and concomitant medications will be coded using the World Health Organization Drug Dictionary (WHO-DD, 01MAR2020 Enhanced) or the latest version in use. Medications will be mapped to the full WHO-DD Anatomical Therapeutic Chemical (ATC) class hierarchy, but PTs will be of primary interest in this analysis.

3.6 Cohorts (Treatment Groups)

Part One (HBeAg-):

- VIR-2218 50 mg
- VIR-2218 100 mg
- VIR-2218 optional cohort, up to 200 mg
- VIR-2218 Overall, for safety data
- Placebo
- Overall

Part Two (HBeAg+):

- VIR-2218 50 mg
- VIR-2218 100 mg
- VIR-2218 optional cohort, up to 200 mg
- VIR-2218 Overall, for safety data
- Placebo
- Overall

For summaries using Safety Analysis Set, the VIR-2218 Overall group will be presented.

4. ANALYSIS SETS

In this SAP, 4 analysis sets are defined: The screened, all randomized, safety, and antiviral analysis sets.

Furthermore, any additional exploratory analysis not identified in the SAP will be identified in the final Clinical Study Report (CSR) as exploratory post hoc analyses, including analyses for additional study populations or subgroups of interest.

The number and percentage of subjects in each analysis set will be summarized by cohort and overall by study part.

4.1 Analysis Set Descriptions

4.1.1 *Screened Analysis Set*

The Screened Analysis Set will consist of all subjects that sign the informed consent form. The listing of Eligibility Criteria will be based on this population.

4.1.2 *All Randomized Analysis Set*

The All Randomized Analysis Set will include all randomized subjects, irrespective of whether they received any study treatment. Subjects will be summarized by the treatment to which they were randomized, regardless of treatment actually received.

Important protocol deviations, demographic and baseline characteristics will be summarized by the All Randomized Analysis Set.

4.1.3 *Safety Analysis Set*

The primary analysis set for safety analyses will be the Safety Analysis Set, which includes all randomized subjects who received at least 1 dose of study treatment. The Safety Analysis Set will be based on actual treatment received if different from the treatment to which they were randomized.

All safety analyses will be based on the Safety Analysis Set.

4.1.4 *Antiviral Activity Set*

The primary analysis set for antiviral activity analyses will be the Antiviral Analysis Set, which includes all subjects in the Safety Analysis Set who have at least 1 non-missing data to provide interpretable results for the specific antiviral activity parameters of interest.

5. SUBJECT DISPOSITION AND ANALYSIS SETS

Outcomes will be summarized by cohort, by study part and overall. All outcomes will be listed by study part and cohort.

5.1.1 *Subject Disposition*

Subject disposition will be summarized using counts and percentages and will be based on the Screened Analysis Set. The number and percentage of subjects who completed the study as planned, subjects discontinued early from the study, as well as the primary reason for early discontinuation will be presented.

All disposition information collected will be listed together with the date that the subject provided informed consent and the date and time of study drug administration.

5.1.2 *Analysis Sets*

The number of subjects included in each of the defined analysis sets will be summarized using counts and percentages and will be based on the Screened Analysis Set.

In addition, each subject's inclusion into/exclusion from each of the defined analysis sets will be listed by the Screened Analysis Set.

6. PROTOCOL DEVIATIONS

Important protocol deviations will be presented for each subject in the by-subject data listings by study part and cohort.

Important protocol deviations will be decided prior to database lock, and may include the deviations from the following, depending on the timing and nature of the deviation:

- Informed Consent Criteria
- Eligibility and Entry Criteria
- Concomitant Medication Criteria
- Laboratory Assessment Criteria
- Study Procedures Criteria
- Serious Adverse Event Criteria
- Randomization Criteria
- Visit Schedule Criteria
- Investigation Product (IP) Compliance
- Efficacy Criteria
- Administrative Criteria
- Source Document Criteria
- Regulatory or Ethics Approvals Criteria
- Other Criteria

7. DEMOGRAPHIC AND BASELINE INFORMATION

Demographic and baseline information will be analyzed using the All Randomized Analysis Set. All summarized information will be presented by cohort, by study part and overall. All demographic information will be listed by cohort and study part.

7.1 Demographics

7.1.1 *Definition of variables*

- Age (years)
- Sex
- Childbearing Potential
- Race
- Ethnicity
- Height (cm)
- Weight (kg)
- Body Mass Index (BMI) (kg/m²)
- HBeAg Baseline Status
- Baseline log10 HBsAg (IU/mL)
- Baseline Alanine Aminotransferase (U/L)
- Baseline HBV DNA Categories (IU/mL) (<10, >=10 and <90, and >=90)

7.1.2 *Biostatistical methods*

Continuous and categorical summaries will be presented for demographic variables as discussed in section 3.1 by cohort, by study part and overall.

7.2 Screening Viral Serology

Viral serology results (Active infection with HIV infection, HCV infection, chronic HBV infection and hepatitis Delta virus infection. Chronic HBV infection is defined as serum HBsAg for > 6 months. In cases of occult HBV, chronic HBV infection is defined as serum HBV DNA positive for > 6 months.) at screening will be listed.

7.3 Medical History

Medical history will be summarized by cohort, by study part and overall if coding using MedDRA® is available. All medical history data will be listed.

HBV Genotype data will be listed.

7.4 Urine Drug Test

Urine drug test results obtained at screening will be listed.

7.5 Cirrhosis Status

Cirrhosis status (FibroScan results and Cirrhosis status) at screening will be summarized by cohort, by study part and overall, and all cirrhosis data collected will be listed.

8. TREATMENT EXPOSURE

Treatment exposure information will be summarized by cohort, by study part and overall using safety population. Duration of Treatment (Days) is calculated as Date of Last Dose - Date of First Dose + 1.

All exposure information will be listed by cohort and study part.

9. PHARMACOKINETICS (PK)

Pharmacokinetic analysis falls outside the scope of the SAP. There will be a separate SAP for PK analyses.

10. PHARMACODYNAMICS (PD)

No PD analysis is planned for this study.

11. EFFICACY

No efficacy analysis is planned for this study.

12. SAFETY

Safety endpoints will be analyzed using the safety analysis set. All information will be presented by cohort, by study part and overall, unless otherwise specified. All safety data will be listed by cohort and study part.

12.1 Adverse Events

12.1.1 *Definition of variables*

- AE
- Serious adverse event (SAE)
- Treatment emergent adverse event (TEAE)

AEs and SAEs are defined in the study protocol. TEAEs are defined as any AEs with an onset date of on or after the study drug start date and no later than 30 days after permanent discontinuation of study drug. If a subject experiences an AE before dosing and after dosing, this AE will be considered as TEAE only if it has worsened in severity. Adverse events that have missing onset dates will be considered treatment-emergent, unless the stop date is known to be prior to the first administration of the study medication. Related AEs are adverse events with relationship as "Related" collected in CRF or missing relationship.

Please refer to section 14 for handling of partial dates for AEs.

12.1.2 *Biostatistical methods*

All AEs will be coded using MedDRA.

AE summary tables will be provided. Summary tables will include the number of subjects (%) experiencing an event and the number of events. Subjects will be counted only once at each SOC and PT level of summary.

The AE, SAE and TEAE summaries will include:

- Overall Summary of all AEs including SAEs
- Overall Summary of TEAEs
- TEAE summary by SOC and PT
- TEAE of Common Terminology Criteria for Adverse Events (CTCAE) Grade ≥ 3 summary by SOC and PT
- Drug related TEAE summary by SOC and PT
- TEAE leading to study withdrawal summary by SOC and PT
- TEAE leading to treatment withdrawal summary by SOC and PT
- Serious TEAE summary by SOC and PT
- Serious TEAE of CTCAE Grade ≥ 3 summary by SOC and PT
- Drug related serious TEAE summary by SOC and PT
- Serious TEAE leading to study withdrawal summary by SOC and PT
- Serious TEAE leading to treatment withdrawal summary by SOC and PT
- SAE summary by SOC and PT
- SAE of CTCAE Grade ≥ 3 summary by SOC and PT
- Drug related SAE summary by SOC and PT

- SAE leading to study withdrawal summary by SOC and PT
- SAE leading to treatment withdrawal summary by SOC and PT
- TEAE leading to death summary by SOC and PT
- Death
- TEAE summary by CTCAE Grade, SOC and PT
- Serious TEAE summary by CTCAE Grade, SOC and PT
- SAE summary by CTCAE Grade, SOC and PT

All AEs will be listed and will include verbatim term, PT, SOC, treatment, severity, causal relationship to the study drug, seriousness, outcome, and action taken with regards to the study drug. Separate listings will be created for AEs leading to study withdrawal and SAEs.

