#### 8.3.1. Adverse Events

Following initiation of study medication, collect all AEs, regardless of cause or relationship, until 12 weeks after last administration of study drug.

All AEs should be followed up until resolution or until the AE is stable, if possible. Sponsor may request that certain AEs be followed beyond the protocol-defined follow-up period.

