### 9.5. Safety Analysis

All safety analyses will be performed using the Safety Analysis Set. Safety will be evaluated by assessment of clinical laboratory tests, physical examinations, ECGs, vital signs measurements at various timepoints during the study, and by the documentation of AEs.

All safety data collected up to 12 weeks after the last study drug administration will be summarized by cohort for each VIR-2218 dose and placebo.

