#### 9.5.1. Adverse Events

Clinical and laboratory AEs will be coded using the Medical Dictionary for Regulatory Activities (MedDRA). System Organ Class (SOC), High-Level Group Term (HLGT), High-Level Term (HLT), Preferred Term (PT), and Lower-Level Term (LLT) will be attached to the clinical database.

Treatment-Emergent Adverse Events (TEAEs) are defined as any AEs with an onset date of on or after the study drug start date and no later than 30 days after permanent discontinuation of study drug.

Summaries (number and percentage of subjects) of TEAEs by SOC and PT will be provided by cohort. TEAEs will also be summarized by relationship to study drug and severity.

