14. HANDLING OF MISSING DATA

All data will be analyzed as collected and missing values will not be imputed nor replaced.

Laboratory data that are continuous in nature but are less than the LLOQ or above the upper limit of quantitation will be imputed to the value of the lower or upper limit minus or plus 1 significant digit, respectively (e.g., if the result of a continuous laboratory test is < 30, a value of 29 will be assigned; if the result of a continuous laboratory test is < 30.0, a value of 29.9 will be assigned).

ALGORITHM FOR TREATMENT EMERGENCE OF ADVERSE EVENTS:

START DATE	STOP DATE	ACTION
Known	Known/Partial/ Missing	If start date < study med start date, then not TEAE If start date >= study med start date and start date <= study med end date + 30, then TEAE
Partial, but known components show that it cannot be on or after study med start date	Known/Partial/ Missing	Not TEAE
Partial, could be on or after study med start date OR Missing	Known	If stop date < study med start date, then not TEAE If stop date >= study med start date, then TEAE
	Partial	Impute stop date as latest possible date (i.e. last day of month if day unknown or 31st December if day and month are unknown), then: If stop date < study med start date, then not TEAE If stop date >= study med start date, then TEAE
	Missing	Assumed TEAE

ALGORITHM FOR PRIOR / CONCOMITANT MEDICATIONS:

START DATE	STOP DATE	ACTION
Known	Known	If stop date < study med start date, assign as prior If stop date >= study med start date and start date <= end of study, assign as concomitant
	Partial	Impute stop date as latest possible date (i.e. last day of month if day unknown or 31st December if day and month are unknown), then: If stop date < study med start date, assign as prior If stop date >= study med start date and start date <= end of study, assign as concomitant
	Missing	If stop date is missing could never be assumed a prior medication If start date <= end of study, assign as concomitant
Partial	Known	Impute start date as earliest possible date (i.e. first day of month if day unknown or 1st January if day and month are unknown), then: If stop date < study med start date, assign as prior If stop date >= study med start date and start date <= end of study, assign as concomitant

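### The SAP drops the protocol's 30-day limit on treatment-emergent laboratory abnormalities without recording it, and its partial-date rule for adverse events lacks an upper limit

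*SAP*

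**What the plan says.** **Laboratory data.** Protocol 9.5.2 calls a laboratory abnormality treatment-emergent if it rises at least one toxicity grade from baseline within 30 days after study drug is permanently stopped. SAP 12.2.1 keeps the one-grade rule but accepts any time after baseline. SAP Section 15, on changes to the planned analysis, says there are none. SAP 12.2.1 also bounds the worst, minimum and maximum post-baseline values by a *reference period* that the SAP does not define. It plans CTCAE-grade shift tables by visit and for the worst value.

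**Late laboratory tests.** Under Protocol Appendix 2 (footnotes c and n), visits after Week 16 take place only in subjects with a fall in HBsAg of at least 1 log10 by Week 16. They run every 4 weeks from Week 20 to Week 48 at most, with liver function tests as the only safety laboratory panel.

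**Adverse events.** SAP 12.1.1 defines TEAEs as "any AEs with an onset date of on or after the study drug start date and no later than 30 days after permanent discontinuation". Protocol 9.5.1 has the same limit: "no later than 30 days after permanent discontinuation of study drug". For a known start date, SAP Section 14 follows it: "If start date >= study med start date and start date <= study med end date + 30, then TEAE". For partial start dates the only check is at the lower end: "Partial, but known components show that it cannot be on or after study med start date". Every other partial or missing start date is settled by comparing the stop date with the first dose, or by assuming a TEAE if the stop date is missing.

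**The concern.** Safety and tolerability is the primary objective, and TEAE incidence and laboratory results are the primary endpoints. Dropping the laboratory limit is an unrecorded departure from the protocol on one of them.

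The consequence is greatest for liver tests. Who is tested after Week 16 depends on response to treatment, so a rule without an end gives responders more time to register an abnormality. Protocol 1.2.2 says NrtIs do not directly affect HBsAg production, so extended follow-up may be expected mainly on VIR-2218. Active and placebo rows would then cover unequal time. The AE tables do not make up for this: Protocol 8.1.1 and 8.1.3 keep laboratory abnormalities out of the AE data when they have no symptoms and need no intervention.

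With the reference period undefined, two programmers could produce different worst-value columns from the same data.

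Under Section 14, the same late AE is or is not a TEAE depending on whether the day of onset was recorded.

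**Working it through.** The plan states no figure to reproduce. The check is date arithmetic on the nominal visit days in Protocol Appendix 2, plus Section 14 applied to test dates.

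**Inputs.** Doses on Day 1 and Day 29; Week 8 = Day 57; Week 12 = Day 85; Week 16 = Day 113; Week 48 = 48 × 7 + 1 = Day 337. AE collection lasts 12 weeks = 84 days after the last dose (Protocol 8.3.1). I take the stopping date and the study medication end date to be the date of the last dose.

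**1. Laboratory counting time, two-dose subject.**
- Protocol limit: 29 + 30 = Day 59. Week 8 is 57 − 29 = 28 days after the last dose (inside); Week 12 is 85 − 29 = 56 days (outside).
- SAP rule, no extended follow-up: 113 − 29 = 84 days.
- SAP rule, followed to Week 48: 337 − 29 = 308 days. Ratio 308/84 = 3.67.

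Scheduled post-baseline visits: Day 2 and Weeks 1–8 make 9; Weeks 12 and 16 bring this to 11; Weeks 20, 24, 28, 32, 36, 40, 44 and 48 add 8, giving 19.

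| Rule | Subject ending at Week 16 | Responder followed to Week 48 |
|---|---|---|
| Protocol 9.5.2 | 30 days, 9 visits | 30 days, 9 visits |
| SAP 12.2.1 | 84 days, 11 visits | 308 days, 19 visits |

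The protocol rule gives every two-dose subject the same counting time; the SAP rule does not.

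**2. Scale.** Each cohort has 4 active subjects, so one extra subject with a late abnormality moves that cohort's incidence by 1/4 = 25 percentage points.

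**3. Partial dates (assumed dates).** First dose 2021-01-04, second dose 2021-02-01, window closes 2021-03-03.
- Onset known as 2021-04-10 (68 days after the last dose): not a TEAE.
- Same event with the day unknown (April 2021) and stop date 2021-04-15: the start could be on or after the first dose and the stop date is after it, so it is a TEAE. Yet the earliest possible onset, 2021-04-01, is 59 days after the last dose.

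**4. Would a fixed 84-day cut repair the laboratory rule?** The second dose may fall on Day 29 ± 2, so the cut falls on Day 111–115. Week 16 is Day 113 ± 7, up to Day 120. Tests within the visit window could be lost. In a one-dose subject the cut is 1 + 84 = Day 85, and Week 16 is lost altogether. The end must be set by visit.

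**The case against.** **Protocol 9.5 may already close the laboratory window.** It says "All safety data collected up to 12 weeks after the last study drug administration will be summarized by cohort". If that governs, tests after Week 16 fall outside the summaries and the unequal time disappears. This is a possible reading, but SAP 12.2.1 does not state it. Even on this reading the SAP counts Weeks 12 and 16, which Protocol 9.5.2 excludes, so the unrecorded departure remains.

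**The shift tables by visit show late grades at their own visits.** This stands as partial mitigation. The incidence table still pools all visits, and the worst-value column still rests on the undefined period.

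**The 308 days and 19 visits are maxima.** This stands. Extended follow-up stops earlier when HBsAg returns towards its Day 1 level, or at the Sponsor's discretion.

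**Partial dates are handled by inclusion, and the effect is small.** Largely right. Nothing is hidden, and Protocol 8.3.1 sites "collect all AEs, regardless of cause or relationship, until 12 weeks after last administration of study drug", which bounds non-serious events in practice. But inclusion by default is meant for doubtful dates. Here the known parts of the date settle the matter, and the result contradicts SAP 12.1.1.

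**A stronger reading.** A reader might infer that the 30-day TEAE window itself breaks the 12-week promise in Protocol 9.5, and that non-serious AEs are lost for 113 − 59 = 54 of 84 days (64%). The documents do not support this. Protocol 9.5.1 sets the same 30 days and promises summaries by SOC/PT, relationship and severity for TEAEs only, which SAP 12.1.2 delivers. Late non-serious events enter the "Overall Summary of all AEs including SAEs", and SAP Section 12 adds "All information will be presented by cohort, by study part and overall, unless otherwise specified". They are also listed in full, and SAEs have their own tables without the 30-day limit. The 64% is a share of days, not of events. Further all-AE tables to 12 weeks would be a preference in a descriptive study of at most 30 subjects.

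**Conclusion.** Two SAP rules are wrong as written and should be corrected before database lock.

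The main one is the laboratory rule. It departs from Protocol 9.5.2 without a record and, taken literally, counts liver-test abnormalities over a period that depends on response: at most 308 days after the last dose against 84, or 19 scheduled visits against 11. The undefined reference period adds to this. A reader might go further and infer a known 3.7-fold imbalance between VIR-2218 and placebo. That does not follow: the ratio compares a responder followed to Week 48 with a subject ending at Week 16, longer follow-up on active drug is an expectation, and the documents give no rate.

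The second is minor. Section 14 lets an AE that is provably outside the window count as a TEAE. How often this would happen is unknown.

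Both faults err towards inclusion, so they distort tables and do not conceal events. The figures assume nominal visit days, two doses and windows counted from the last dose; the calendar dates in the example are invented.

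**What to change.** In the SAP only, before database lock and unblinding:

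1. In 12.2.1, restore the 30-day limit of Protocol 9.5.2 for the treatment-emergent laboratory incidence table, and state the date from which it is counted.
2. Add a supplementary version through the Week 16/early termination visit. Define its end by visit and not by a fixed 84 days, so that in-window Week 16 tests and one-dose subjects are kept. Define the reference period with the same end.
3. Show liver-test grade increases after Week 16 separately, for extended follow-up subjects only.
4. Add a row to Section 14: if the known parts of a partial start date place onset more than 30 days after the last dose, the event is not a TEAE.
5. Record in Section 15 any departure from Protocol 9.5.2 that remains.

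The cost is one extra laboratory table, one separate display, one algorithm row and some text, with no new data and no protocol amendment. Both added outputs will be sparse. Restoring a limit by date can also drop a Week 8 test taken late in its window after an early second dose (Day 59 − Day 27 = 32 days); the supplementary table keeps it. All-AE tables by SOC/PT, grade and relatedness to 12 weeks are optional.

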2.3 Endpoints

2.3.1 Primary endpoints

- Incidence of treatment-emergent adverse events (TEAEs).
- Clinical assessments including but not limited to laboratory test results.

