15. CHANGES TO THE PLANNED ANALYSIS

Not applicable.

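### SAP 12.1.1 and the known-date row of SAP 14 give inconsistent treatment-emergence rules for adverse events that already occurred before dosing

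*SAP*

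**What the plan says.** Protocol 9.5.1 has TEAEs "defined as any AEs with an onset date of on or after the study drug start date", with the window closing 30 days after study drug is permanently stopped. It does not mention severity or an earlier occurrence of the same event.

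SAP 12.1.1 repeats that date window and then adds a second sentence, that if a subject "experiences an AE before dosing and after dosing, this AE will be considered as TEAE only if it has worsened in severity". It sends the reader to Section 14 for partial dates only.

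SAP 14 nevertheless carries a full algorithm for treatment emergence, and its first row rules on AEs whose start date is known. A start before study drug is settled by "If start date < study med start date, then not TEAE". A later start is settled by "If start date >= study med start date and start date <= study med end date + 30, then TEAE". The row contains neither a worsening test nor a check for a pre-dose occurrence.

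No text says which of the two SAP sections governs. SAP 15, on changes to the planned analysis, reads "Not applicable".

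**The concern.** TEAE incidence is a primary endpoint (Protocol 3.1, SAP 2.3.1), and the TEAE flag also feeds most of the AE tables listed in SAP 12.1.2. For AEs with a pre-dose history, that flag can depend on which SAP section the programmer follows. Following 12.1.1 can exclude a post-dose episode that meets the protocol definition. Following 14 excludes an on-treatment worsening that stays on its original record. Either choice lowers the reported incidence. The severity test is also absent from the protocol and is not declared as a change.

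**Working it through.** **Inputs**
- Cohorts of 5 randomized 4:1, with two planned cohorts and one optional cohort in each of two Parts (Protocol 4.1, SAP 2.1).
- Doses on Day 1 and Week 4 (Day 29).
- TEAE window from first dose to last dose + 30 days. I treat permanent discontinuation in Protocol 9.5.1 and the study medication end date in SAP 14 as the same day, so with both doses given the window closes on Day 29 + 30 = Day 59.

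**Plan's own figure.** 2 Parts × 3 cohorts × 5 = 30, which matches the stated maximum. The planned cohorts alone give 2 × 2 × 5 = 20.

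**Rules side by side.** For known dates, SAP 14 gives the same result as Protocol 9.5.1. SAP 12.1.1 is shown under two readings of *only if*. In the first, worsening decides the matter for any AE seen before and after dosing. In the second, worsening is a further condition on top of the onset window. Both columns let the sentence cover recurrences as well as continuous events.

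| Event | Protocol 9.5.1 and SAP 14 | SAP 12.1.1, worsening decides | SAP 12.1.1, added condition |
|---|---|---|---|
| A. No pre-dose occurrence, onset Day 10 | TEAE | TEAE | TEAE |
| B. Pre-dose AE resolves, recurs Day 10, not worse | TEAE | not TEAE | not TEAE |
| C. Pre-dose AE resolves, recurs Day 10, worse | TEAE | TEAE | TEAE |
| D. One record from before dosing, worsens Day 10 | not TEAE | TEAE | not TEAE |
| E. One record from before dosing, same grade | not TEAE | not TEAE | not TEAE |
| F. No pre-dose occurrence, onset Day 60 | not TEAE | not TEAE | not TEAE |

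The sections conflict in B under both columns and in D under the first column. In D under the second column they agree, and both miss the worsening.

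**Size.** Suppose the reclassified event is the subject's only TEAE. Incidence in a group of n then moves by 100/n points:
- dose cohort, n = 4: 100/4 = 25
- VIR-2218 Overall within a Part, n = 2 × 4 = 8: 100/8 = 12.5; with the optional cohort, n = 12: 100/12 = 8.3
- placebo within a Part, n = 2: 100/2 = 50; with the optional cohort, n = 3: 100/3 = 33.3

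**How many subjects.** Protocol 8.3 limits pre-dose AE records to events tied to study procedures, and SAEs. Other screening events go to medical history (Protocol 7.2). The documents give no AE rates, so the number affected cannot be computed. A plausible instance of B, by inference only, is a blood-sampling reaction at screening that returns at a later visit, since samples are drawn throughout follow-up.

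**The case against.** A reader might infer that the two sections state opposite rules and that an ordinary new post-dose AE could drop out of the primary endpoint. The documents do not support that: rows A and F show full agreement when there is no pre-dose occurrence.

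A reader might also take disagreement in both directions as certain. It is not.
- The SAP 12.1.1 sentence could be confined to one continuous event spanning first dose, which would put row B outside it. This is possible but not the natural reading. A continuous event kept as one record fails the onset window anyway, so on this reading the sentence either does nothing or admits worsened events and so conflicts with SAP 14 in row D.
- The row D conflict needs worsening to override the onset window, and needs the worsening to stay on a record with its original onset date. Neither document settles these points.

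The scope is narrow, and that part of the objection stands. Protocol 8.1.1 already makes a worsening of a condition held in medical history an AE in its own right. If it is dated at the worsening, which is an assumption, both sections count it. The eligibility criteria also make a subject with a significant screening SAE less likely to be dosed.

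No event disappears from the report. SAP 12.1.2 lists every AE, summarizes all AEs, and plans SAE tables not restricted to TEAEs. The analysis is descriptive, so no test result changes.

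Finally, the point shifts are what any one-subject change produces in groups this small. They show sensitivity and say nothing about how often the conflict will arise.

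**Conclusion.** The inconsistency is real, limited to AEs with a pre-dose occurrence, and worth correcting because a primary-endpoint flag should have one executable definition. The same-grade recurrence is the firmer case: on the natural reading, SAP 12.1.1 excludes an event that Protocol 9.5.1 and SAP 14 include. The worsening of a single pre-dose record is conditional. Either SAP 12.1.1 counts it and SAP 14 does not, or both miss it.

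Few subjects are likely to be affected. The shifts shown (25 points per dose cohort, 12.5 or 8.3 for VIR-2218 Overall per Part, 50 or 33.3 for placebo per Part) hold only where the event is the subject's sole TEAE. They also assume full 4:1 cohorts with every randomized subject dosed.

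**What to change.** Before database lock and unblinding, use one governing rule in both SAP 12.1.1 and the first row of the SAP 14 table:

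- An AE record with onset from first dose to last dose + 30 days is a TEAE, as in Protocol 9.5.1, whether or not the same term occurred before dosing.
- An AE record that began before first dose and increases in CTCAE grade within that window is also a TEAE, dated at the worsening.
- A worsening of medical history already entered as a new AE under Protocol 8.1.1 is counted once, by its own onset date. This prevents double counting.

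The second item goes beyond Protocol 9.5.1, so declare it in SAP 15 as a change from the protocol. SAP 12.1.1 should also say that Section 14 applies to known dates as well as partial ones.

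The cost is a few lines of SAP text and one programming condition. TEAE counts may rise slightly, and some of the added events may be procedure-related recurrences.
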